7.4 Dose Modification Guidance and Safety Stopping Criteria

7.4.1 Dose Escalation Part (GEN3009 Monotherapy)

If a subject experiences a DLT, the subject may continue treatment with GEN3009, if the toxicity recovers to \leq Grade 2 or baseline within 4 weeks from occurrence of the DLT. Continued administration of GEN3009 must be agreed to between the sponsor and the investigator based on a thorough assessment of the event, the duration of the event, and benefit-risk for the subject. In the event a subject experiences a second episode of a DLT with GEN3009, the treatment will be permanently discontinued. Treatment with GEN3009 will be discontinued in the event the DLT is not resolved within 4 weeks.

- If a subject experiences toxicity that qualifies as a DLT but occurs after the 4-week DLT evaluation period, the subject's benefit-risk must be thoroughly assessed. Continued treatment with GEN3009 must be agreed between the sponsor and the investigator.
- For the subject who receives more than 4 doses of GEN3009, ie, treatment beyond the DLT evaluation period, all corresponding AEs that meet the DLT criteria will be considered for the purpose of determining the MTD and/or the RP2D. For the declaration of the RP2D of GEN3009 in the Expansion and for further development, the totality of the data from Dose Escalation (including safety, PK, pharmacodynamics, and preliminary efficacy will be evaluated).
- During the trial, a planned dose of GEN3009 can be postponed for up to 4 weeks from the last dose of trial drug for an AE whether it is considered drug-related or not.
- In case of dose delay of more than 4 weeks from the last trial drug administration due to toxicity, GEN3009 should be discontinued, unless approved by the sponsor's medical monitor.
- During the trial, the GEN3009 dose can be held for the following laboratory results:
 - a. If platelet count $<50 \times 10^9/L$, hold dose until platelet count is $\geq 50 \times 10^9/L$.
 - b. If febrile neutropenia $<0.5 \times 10^9/L$, hold dose until neutrophil count is $\geq 0.5 \times 10^9/L$.
 - c. If hemoglobin is <8 g/dL (<5 mmol/L), hold dose until hemoglobin ≥ 8 g/mL (>5 mmol/L).

Note: If the investigator deems any of the above cytopenia as bone marrow involvement due to the disease, continuation of GEN3009 treatment can be discussed with the sponsor's medical monitor. Transfusion with blood products and/or administration with G-CSF is permitted if needed (refer to Section [6.6.1](#)).

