7.4.3.1 Cytopenias (All Cohorts)

GEN3009 and/or GEN3013 dose (regardless of being monotherapy or combination therapy) will be held for up to 4 weeks for the following hematologic laboratory results:

Table 25 Dose Modification Rules for Cytopenias

Laboratory Parameter	Laboratory Value	
	Hold GEN3009 and/or GEN3013 Dose	Resume GEN3009 and/or GEN3013 Dose
Platelet count ^a	<50 × 10 ⁹ /L	≥50 × 10 ⁹ /L
Neutrophil count	<0.5 × 10 ⁹ /L	≥0.5 × 10 ⁹ /L
Hemoglobin	<8 g/dL (<5 mmol/L)	≥8 g/dL (>5 mmol/L)

No dose-reduction is allowed for GEN3009 or GEN3013, but a repriming cycle may be needed if the interval between the previous dose of GEN3013 and next planned dose exceeds 6 weeks.

a. In subjects with CLL having platelets ≥30×10⁹/L (30,000/µL) can be dosed after the consultation with the sponsor's medical monitor.

Note: If the investigator deems any of the above cytopenias are secondary to bone marrow involvement by the disease, continuation of study treatment can be discussed with the sponsor's medical monitor. Transfusion with blood products (eg, RBC, platelets) and/or administration with G-CSF is permitted if needed. G-CSF must be used in case of ≥Grade 3 neutropenia during Dose Escalation and safety run in parts of the study. See Sections 6.6.1 and 7.5.1.

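### Sections 7.4.1 and 7.4.3.1 (Table 25) both cover Dose Escalation but give different dose-hold instructions for afebrile neutrophils below 0.5 x 10^9/L and for CLL platelets of 30 to below 50 x 10^9/L

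*Protocol*

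**What the plan says.** Protocol Section 7.4.1 (Dose Escalation Part) introduces its hold list with "During the trial, the GEN3009 dose can be held for the following laboratory results". Three items follow:

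- Item a holds for platelets below 50 x 10^9/L until they reach at least 50.
- Item b begins "If febrile neutropenia", sets the level at 0.5 x 10^9/L, and holds until the neutrophil count is back to at least 0.5.
- Item c covers hemoglobin below 8 g/dL.

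A note to the list lets continued treatment be discussed with the medical monitor when the investigator attributes a cytopenia to marrow involvement. It adds "Transfusion with blood products and/or administration with G-CSF is permitted if needed" and points to Section 6.6.1.

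Section 7.4.3.1 is headed as applying to all cohorts. Its instruction covers both drugs: "dose (regardless of being monotherapy or combination therapy) will be held for up to 4 weeks for the following hematologic laboratory results". Under that sentence, Table 25 gives a neutrophil trigger below 0.5 x 10^9/L with no fever condition, and a platelet trigger below 50. Footnote a lets CLL subjects with platelets of at least 30 be dosed after consultation with the medical monitor. The note carries the same marrow-involvement route and adds "G-CSF must be used in case of" Grade 3 or higher neutropenia in Dose Escalation and the safety run-in.

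**The concern.** A Dose Escalation subject falls under both sections. Section 9.4.1 has the investigator review hematology before every administration and dose according to the protocol's instructions, so a site meets the two sets of rules each time it doses. If sites follow different sections, subjects with the same laboratory result will be handled differently.

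That matters for more than consistency of care:

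- Dose interruptions, delays and dose intensity are primary endpoints in Dose Escalation (Table 17).
- The neutropenia DLT in Section 7.2 is Grade 4 (below 0.5 x 10^9/L) lasting more than 7 days, which is the Table 25 cut-off. Cycle 1 dosing is weekly, so the decision to give or withhold the next dose can fall inside that period.
- Section 4.4.3 applies a 33% stopping threshold to the same event in subjects past the DLT period.
- Under Table 22, with 3 evaluable subjects, one DLT changes the decision from escalate to remain, and two change it to de-escalate.

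**Working it through.** The plan gives no figure to reproduce here, so the check is a comparison of text. All counts are x 10^9/L.

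| Dose Escalation case | Section 7.4.1 | Section 7.4.3.1, Table 25 |
|---|---|---|
| Neutrophils below 0.5, febrile | Hold item b met | Hold |
| Neutrophils below 0.5, afebrile | No hold item met | Hold |
| CLL, platelets 30 to below 50, attributed to marrow | Hold item a; continuation may be discussed with the medical monitor | May be dosed after consultation |
| CLL, platelets 30 to below 50, not attributed to marrow | Hold item a, no exception | May be dosed after consultation |
| Lead-in verb | *can* | *will* |
| Hemoglobin resume level | 8 g/mL | 8 g/dL |

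Rows 2 and 4 are the substantive conflicts. Row 4 describes subjects who can be in the trial: Section 5.1.1 admits CLL subjects with platelets of at least 30.

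**Does the verb change the result?** Take 7.4.1 both ways.

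- If the items are imperative (each says to hold), the *can*/*will* difference largely disappears, and rows 2 and 4 stand.
- If *can* makes the list discretionary, row 4 weakens, because 7.4.1 no longer forbids dosing a CLL subject at 30 to below 50. Row 2 stands, and a required hold in Table 25 becomes optional in 7.4.1 for all three parameters.

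The neutrophil conflict survives either reading.

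**Is there a rule of precedence?** None was found. Section 7.4.1 does not refer to 7.4.3.1, and 7.4.3.1 does not refer to 7.4.1. Section 6.6.1 points to 7.4.3, but for permitted and required treatments, not for dose holds.

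**Hemoglobin unit.** Section 5.1.1 equates 9.0 g/dL with 5.6 mmol/L, so 8 g/dL = 8 x 5.6 / 9.0 = 4.98 mmol/L. That agrees with the 5 mmol/L printed in item c, so g/mL is a unit slip.

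**G-CSF.** Section 7.4.1 refers to 6.6.1, which mandates growth factors at Grade 3 or higher neutropenia in Dose Escalation. Section 7.5.1 and the Table 25 note say the same. There is no conflict.

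**How many subjects?** Section 2.1.4.1 reports neutropenia in 94.4% of 18 subjects: 0.944 x 18 = 17.0, so 17 subjects. No grade is given. The conflict needs a count below 0.5, no fever, and a scheduled dose, and that share is not reported.

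**DLT evaluability.** Protocol Section 11.1.2 requires 80% to 125% of the planned dose and completion of the DLT period, unless a DLT occurs or the subject discontinues for toxicity. Assume four equal Cycle 1 doses with one omitted because of a hold: 3/4 = 75%, below 80%, and the subject drops out of the dose-determining set. A dose that is delayed but still given inside the window leaves 4/4 = 100% and has no such effect.

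**The case against.** The strongest reply is that the neutrophil rules can be obeyed together. Section 7.4.1 does not tell anyone to dose at a neutrophil count below 0.5; it is silent on the afebrile case, and a site that reads all of Section 7 would hold under Table 25. That is fair as logic. It does not remove the problem, because 7.4.1 is the section labelled for Dose Escalation, its list is specific, and limiting the neutrophil item to febrile cases invites the inference that other cases need no hold. Nothing sends the reader on to Table 25 for holds.

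On platelets, both sections route through the medical monitor, and the 7.4.1 note already covers cytopenia due to marrow involvement. This stands, and it narrows the platelet conflict to CLL subjects whose low count is not so attributed.

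A reader might also infer that the G-CSF rules conflict, setting "Transfusion with blood products and/or administration with G-CSF is permitted if needed" against "G-CSF must be used in case of" Grade 3 or higher neutropenia. The documents do not support that. The 7.4.1 sentence carries a reference to Section 6.6.1, where the mandate sits, and the Table 25 note itself has a similar permissive sentence just before its mandate.

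**Conclusion.** The point stands as an internal inconsistency in dose-hold instructions. The neutrophil trigger is the main conflict, and the CLL platelet rule is a second, narrower one. The *can*/*will* difference and the hemoglobin unit are secondary wording points.

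Its size cannot be stated. A reader might infer from the 94.4% that nearly all subjects are affected. That does not follow: the figure has no grade attached, Section 2.1.4.1 reports that counts had usually recovered before the next dose, and Section 4.3.2 says G-CSF given at onset of Grade 3 or 4 neutropenia was enough for recovery by then.

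A reader might also infer that the DLT rate and MTD depend on which section a site follows. That is a possibility, not a finding: no DLT had been observed in the 18 evaluated subjects, and G-CSF is mandated under either section. The loss of evaluability at 75% rests on the assumptions of four equal doses, one of them omitted and not merely delayed, and the protocol's definition of the dose-determining set. What is established is that the same laboratory result leads to different instructions for the same subject.

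**What to change.** Reconcile Sections 7.4.1 and 7.4.3.1 so that a single set of cytopenia hold instructions applies to Dose Escalation, or state which section governs there. The reconciled text should settle four things: whether fever is part of the neutrophil trigger, whether the hold is required or discretionary, how CLL subjects with platelets of 30 to below 50 x 10^9/L are handled, and how the marrow-involvement note fits with that. Correct the hemoglobin resume unit in 7.4.1 item c. Which clinical rule applies is for the sponsor to decide; this review does not favor either section.

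The cost is protocol wording and a site memo. No sample size, endpoint definition or analysis changes. Because Sections 2.1.4.1 and 4.3.1 add higher dose levels, the clarification would reach subjects still to be dosed.

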7.4.2 Expansion Part (Including Safety Run-in)

7.4.2.1 GEN3009 Dose Modification Rules

Dose reduction is not allowed for GEN3009.

Dose delay is allowed for GEN3009 for the management of toxicities. GEN3009 administration can be postponed up to 4 weeks from the next scheduled date.

- If a dose is delayed more than 4 weeks from the next scheduled dosing date due to toxicity, GEN3009 should be discontinued, unless approved by the sponsor's medical monitor.
- If a GEN3009 dose is delayed or withheld for any reason, GEN3013 may be continued, if clinically indicated, after consultation with the sponsor's medical monitor.
- If GEN3009 is discontinued, GEN3013 can be continued if approved by the sponsor's medical monitor.

7.4.2.2 GEN3013 Dose Modification Rules

Dose reduction is not allowed for GEN3013 on an individual subject level in this trial. Refer to Section [4.3](#) for dosing rationale.

If a dose is delayed more than 6 weeks, the subject should be asked to perform an unscheduled visit for collection of AEs, concomitant medications, laboratory values (including hematology, biochemistry, and coagulation values), and a limited physical examination (as clinically indicated) after consultation with the sponsor's medical monitor.

A repriming cycle is necessary if dose is delayed at certain time points, as described below. A repriming cycle consists of a weekly schedule of a priming dose, intermediate dose, and 2 full doses. Refer to [Table 15](#) for the repriming cycle Visit Assessment Schedule.

A repriming cycle should occur:

- For the second GEN3013 full dose onward (ie, C2D1), if the interval between the previous dose of GEN3013 and next planned dose exceeds 6 weeks.

During the repriming cycle, CRS prophylaxis must be resumed with 3 consecutive days of corticosteroids beginning at each GEN3013 dose, until at least 1 full dose of GEN3013 is administered without subsequent occurrence of CRS Grade ≥ 2 (see Section [6.2.2](#)).

Once the full repriming cycle is completed, the subject should resume treatment with Day 1 of the next planned cycle (subsequent to the cycle during which the dosing was delayed). For example, if the subject experiences a 7-week delay after C3D1, the subject should receive a repriming cycle, then continue treatment at C4D1. GEN3009 dose will continue as scheduled.

If GEN3013 dose is delayed, withheld, or discontinued during the combination treatment period, GEN3009 can be continued if approved by the sponsor's medical monitor.

Refer to Section [7.4.3](#) for information about dose modifications due to AEs.

7.4.3 Dose Modification Guidelines for Toxicity Management

Refer to Section 6.2.1 and Section 6.2.2 for requirements on premedication, and Section 6.3, Section 6.6.1, Section 7.5, Appendix 13, and Appendix 14 for guidance on prevention and management of specific AEs.

7.4.3.1 Cytopenias (All Cohorts)

GEN3009 and/or GEN3013 dose (regardless of being monotherapy or combination therapy) will be held for up to 4 weeks for the following hematologic laboratory results:

Table 25 Dose Modification Rules for Cytopenias

Laboratory Parameter	Laboratory Value	
	Hold GEN3009 and/or GEN3013 Dose	Resume GEN3009 and/or GEN3013 Dose
Platelet count ^a	<50 × 10 ⁹ /L	≥50 × 10 ⁹ /L
Neutrophil count	<0.5 × 10 ⁹ /L	≥0.5 × 10 ⁹ /L
Hemoglobin	<8 g/dL (<5 mmol/L)	≥8 g/dL (>5 mmol/L)

No dose-reduction is allowed for GEN3009 or GEN3013, but a repriming cycle may be needed if the interval between the previous dose of GEN3013 and next planned dose exceeds 6 weeks.

a. In subjects with CLL having platelets ≥30×10⁹/L (30,000/µL) can be dosed after the consultation with the sponsor's medical monitor.

Note: If the investigator deems any of the above cytopenias are secondary to bone marrow involvement by the disease, continuation of study treatment can be discussed with the sponsor's medical monitor. Transfusion with blood products (eg, RBC, platelets) and/or administration with G-CSF is permitted if needed. G-CSF must be used in case of ≥Grade 3 neutropenia during Dose Escalation and safety run in parts of the study. See Sections 6.6.1 and 7.5.1.

7.4.3.2 Cytokine Release Syndrome (the GEN3009 + GEN3013 Combination Cohort)

CRS has been reported with the use of GEN3013. To date, CRS is not a known/identified risk with GEN3009. Refer to Section 7.5.2 and Appendix 13 for guidelines for grading and supportive care for CRS management.

CRS must be graded according to the ASTCT grading for CRS (Lee et al., 2019).

Table 26 GEN3013 Dose Modification for Cytokine Release Syndrome (GEN3009 + GEN3013 Combination Cohort)

CRS	
ASTCT Grade	Dose Modification
Grade 1	
Hold GEN3013 (and GEN3009 if given in combination) until resolution of CRS event and treat the subject (see Appendix 13)
Grade 2	
Hold GEN3013 (and GEN3009 if given in combination) until resolution of CRS event and treat the subject.If Grade 2 or higher CRS occurs with the second full dose or beyond, administer CRS prophylaxis with the next dose until a GEN3013 dose is given without subsequent CRS (of any grade)
Grade 3 lasting less than 72 hours	
Hold GEN3013 (and GEN3009 if given in combination) until resolution of CRS event and treat the subject.Continue with the next planned GEN3013 dose at the planned date and hospitalize the subject for at least 72 hours following this GEN3013 administration.If Grade 2 or higher CRS occurs with the second full dose or beyond, administer CRS prophylaxis with the next dose until a GEN3013 dose is given without subsequent CRS (of any grade)
Grade 3 lasting longer than 72 hours	
Permanently discontinue administration of GEN3013 and treat the subject (see Appendix 13)
Grade 3, second occurrence (ie, 2 separate Grade 3 events)	
Permanently discontinue administration of GEN3013 even if each event resolved to Grade 2 within 72 hours, and treat the subject (see Appendix 13)
Grade 4 CRS	
Permanently discontinue administration of GEN3013 and treat the subject (see Appendix 13)

7.4.3.3 Tumor Lysis Syndrome (All Cohorts)

In cases of TLS, hold GEN3009 and/or GEN3013 (regardless of being monotherapy or combination therapy) until the TLS has resolved.

TLS should be reported as an AE, using the National Cancer Institute Common Terminology Criteria for Adverse Events (CTCAE) Version 5.0 grading, whereas clinical TLS should be reported as an AESI, using Cairo-Bishop grading (see [Appendix 4](#)).

Refer to Section [7.5.4](#) for prevention and management of TLS.

7.4.3.4 Immune Effector Cell-Associated Neurotoxicity Syndrome (GEN3009 + GEN3013 Combination Cohort)

ICANS has been reported with the use of GEN3013. To date, ICANS is not a known/identified risk with GEN3009. See [Table 27](#) for information on GEN3013 dose modification for ICANS. Refer to Section 7.5.3 for supportive care and Appendix 13 grading of ICANS.

Table 27 GEN3013 Dose Modification for ICANS (GEN3009 + GEN3013 Combination Cohort)

ICANS	
ASTCT Grade	Dose Modification
Grade 1 or 2	
Hold GEN3013 (and GEN3009 if given in combination) until resolution of ICANS to Grade 0 and treat the subject appropriately.
Grade 3 or 4	
Permanently discontinue administration of GEN3013 and treat the subject appropriately.

7.4.3.5 All Other AEs Related to GEN3009 and/or GEN3013

Relationship assessment will be based on the Investigator's judgement.

Table 28 Dose Modification for All Other GEN3009 and/or GEN3013-Related AEs

CTCAE Grade	Dose Modification
Grade 1	
Continue study drug
Grade 2	
Continue study drug
Grade 3*	
First episode: May hold treatment until improvement to \leq Grade 2 or resolution to baseline.Second episode of the same AE considered related to study drug: Hold treatment until improvement to \leq Grade 2 or resolution to baseline and permanently discontinue if no improvement within 14 days unless otherwise agreed upon with the sponsor's medical monitor.
Grade 4 ^a	
First episode: Hold treatment until improvement to \leq Grade 2 or resolution to baseline.Second episode of same AE considered related to study drug: Permanently discontinue study drug unless otherwise agreed upon with the sponsor's medical monitor.

a. This may exclude any asymptomatic isolated laboratory abnormalities without any clinical consequences such as hypoalbuminemia, hypophosphatemia, hyponatremia, etc.

7.5 Management of Specific Adverse Events

7.5.1 Neutropenia and Other Cytopenias (All Cohorts)

G-CSF and other hematopoietic growth factors may be used in the management of acute toxicity, such as febrile neutropenia and neutropenia, when clinically indicated or at the investigator's discretion.

- In case of \geq Grade 3 neutropenia, use of growth factors is mandated during Dose Escalation and Safety Run-in parts of the study.

Neutropenic fever should be evaluated immediately for any potential underlying reason (eg, blood cultures, imaging, etc) and managed based on local institutional guidelines ensuring appropriate anti-infective prophylaxis.

For other cytopenias, blood or platelet transfusion should be given based on local institutional guidelines.

Complete blood counts should be monitored until count recovery.

7.5.2 Supportive Care for Cytokine Release Syndrome (Expansion GEN3009 + GEN3013 Combination Cohort Only)

Rescue medication in terms of an antidote to reverse the action of GEN3013 is not available. Potential adverse effects of GEN3013 have to be treated symptomatically. For treatment of CRS patients should receive supportive care according to [Appendix 13](#).

The supportive care can include, but is not limited to:

- Infusion of saline
- Systemic glucocorticosteroid, antihistamine, antipyretic
- Support for blood pressure (vasopressin, vasopressors)
- Support for low-flow and high-flow oxygen and positive pressure ventilation
- Monoclonal antibody against IL-6R, IL-6 or IL-1 (eg, tocilizumab, siltuximab, and/or anakinra)
- Blood product support, analgesics, skin and mouth care, etc, should be according to local guidelines and investigator's discretion.

7.5.3 Supportive Care for Immune Effector Cell-Associated Neurotoxicity Syndrome (Expansion GEN3009 + GEN3013 Combination Cohort Only)

Close monitoring of mental status during treatment is important to secure a timely start of supportive care as needed. Supportive care can include, but is not limited to:

- Initiation of IV hydration
- Withhold oral intake
- Avoid medications that cause central nervous system depression
- Initiation of corticosteroids
- Anti-cytokine therapy
- Anti-convulsive therapy

7.5.4 Tumor Lysis Syndrome Prevention and Management (All Cohorts)

To prevent TLS, all subjects should receive appropriate hydration and allopurinol according to local standards or available guidelines ([Coiffier et al., 2008](#)). Subjects who are considered to have an increased risk for TLS, eg, due to the type of lymphoma, the tumor burden (bulky disease and/or elevated lactate dehydrogenase), renal impairment and/or elevated uric acid should be considered for hydration and prophylactic treatment with a uric acid-lowering agent as well as frequent monitoring. If signs of TLS occur, supportive therapy, including rasburicase, may be used as clinically indicated at the investigator's discretion. In addition, close monitoring of laboratory parameters to allow for early diagnosis of a possible TLS is recommended.

For details, refer to [Table 4](#) and [Table 15](#) for the minimum sampling time points for tumor lysis. Definition of TLS and guidance for grading of TLS events are provided in [Appendix 4](#).

7.5.5 Tumor Flare Reaction Management (All Cohorts)

Subjects in this trial should be monitored for tumor flare reaction (TFR). TFR is defined as a sudden and tender increase in the size of the disease-bearing sites, including the lymph nodes, spleen and/or the liver often accompanied by low-grade fever, diffuse rash, and in some cases increase in the peripheral blood lymphocyte counts. TFR will be assessed according to the following criteria:

- Grade 1: Mild pain not interfering with function
- Grade 2: Moderate pain; pain or analgesics interfering with function, but not interfering with activities of daily living (ADL)
- Grade 3: Severe pain; pain or analgesics interfering with function and interfering with ADL
- Grade 4: disabling
- Grade 5: death

Treatment of TFR is up to the discretion of the investigator depending upon the severity and clinical situation. It is suggested that \geq Grade 2 TFR be treated with corticosteroids at the investigator's discretion. NSAIDs (ie, ibuprofen 400 to 600 mg orally every 4 to 6 hours as needed) and/or narcotic analgesics for pain management may also be administered as needed. In mild to moderate cases, it is suggested that GEN3009 and/or GEN3013 be continued along with symptomatic treatment as indicated above.

